12.4.1 Analysis of Primary Effectiveness Endpoint(s)

[figure not shown]
The primary objective of this study is to demonstrate safety and effectiveness of [REDACTED] soft contact lens when worn for daily wear as compared to Biofinity soft contact lens.

The primary effectiveness endpoint is distance VA with study lenses, collected in Snellen, for each eye. Conversion will be made to the logMAR scale.

12.4.1.1 Statistical Hypotheses

No hypothesis testing of the primary effectiveness endpoint is planned.

12.4.1.2 Analysis Methods

Summary statistics will be provided. 

Topic	Percentage
The Internet	95
Smartphones	92
Cloud Computing	88
Big Data	85
Machine Learning	82
Blockchain	78
Artificial Intelligence	75
Quantum Computing	72
The Internet	95
Smartphones	92
Cloud Computing	88
Big Data	85
Machine Learning	82
Blockchain	78
Artificial Intelligence	75
Quantum Computing	72
The Internet	95
Smartphones	92
Cloud Computing	88
Big Data	85
Machine Learning	82
Blockchain	78
Artificial Intelligence	75
Quantum Computing	72
The Internet	95
Smartphones	92
Cloud Computing	88
Big Data	85
Machine Learning	82
Blockchain	78
Artificial Intelligence	75
Quantum Computing	72

12.5 Handling of Missing Data

All data obtained in evaluable subjects/eyes will be used. No imputation for missing values will be carried out.

Incidence and reasons for discontinuation by lens group will be tabulated at each visit and overall.

13 DATA HANDLING AND ADMINISTRATIVE REQUIREMENTS

13.1 Subject Confidentiality

[figure not shown]
The Investigator must ensure that the subject's anonymity is maintained throughout the course of the study. In particular, the Investigator must keep an enrollment log with confidential identifying information that corresponds to the subject numbers and initials of each study participant. [REDACTED]

Education Level	Percentage
Less than primary	35.0
Primary	32.0
Secondary	25.0
Postsecondary	18.0

13.2 Completion of Source Documents and Case Report Forms

The nature and location of all source documents will be identified to ensure that original data required to complete the CRFs exist and are accessible for verification by the site monitor, and all discrepancies shall be appropriately documented via the query resolution process. Site monitors are appointed by the Study Sponsor and are independent of study site staff.

13.3 Data Review and Clarifications

A review of CRF data to the subject's source data will be completed by the site monitor to ensure completeness and accuracy. After the CRFs have been completed, additional data clarifications and/or additions may be needed as a result of the data cleaning process. Data clarifications are documented and are part of each subject's CRF.

13.4 Sponsor and Monitoring Responsibilities

The Study Sponsor will designate a monitor to conduct the appropriate site visits at the appropriate intervals according to the study monitoring plan. The clinical investigation will be monitored to ensure that the rights and well-being of the subjects are protected, the reported data are accurate, complete, and verifiable from the source documents, and the study is conducted in compliance with the current approved protocol (and amendments[s], if applicable), with current GCP, and with applicable regulatory requirements.

The site may not screen subjects or perform the informed consent process on any subject until it receives a notification from an appropriate Study Sponsor representative that the site may commence conducting study activities. Monitoring will be conducted periodically while the clinical study is ongoing. Monitoring methods may include site visits, telephone, written and fax correspondence. Close-out visits will take place after the last visit of the last subject at the site.

A Coordinating Investigator may be identified by the Study Sponsor to review and endorse the final study report. In cases where a Coordinating Investigator is engaged, the Study Sponsor will select the Coordinating Investigator based upon their experience, qualifications, active study participation, and their willingness and availability to take on this role.

13.5 Regulatory Documentation and Records Retention

The Investigator is required to maintain up-to-date, complete regulatory documentation as indicated by the Study Sponsor and the Investigator's files will be reviewed as part of the ongoing study monitoring.

13.6 Quality Assurance and Quality Control

The Study Sponsor will secure agreement from all involved parties to ensure direct access to all study related sites, source data and documents, and reports for the purpose of monitoring and auditing by the Study Sponsor, and inspection by domestic and foreign regulatory authorities. Quality control will be applied to each stage of data handling to ensure that all data are reliable and have been processed correctly. Agreements made by the Study Sponsor with the Investigator/Institution and any other parties involved in the clinical study will be provided in writing as part of the protocol or as a separate agreement.

14 ETHICS

The Investigator must ensure that all personnel involved in the conduct of the study are qualified to perform their assigned responsibilities through relevant education, training, and experience. The Investigator and all clinical study staff must conduct the clinical study in compliance with the protocol. Deviations from this protocol, regulatory requirements and/or GCP must be recorded and reported to the Sponsor prior to database lock. If needed, corrective and preventive action should be identified, implemented, and documented within the study records. Use of waivers to deviate from the clinical protocol is prohibited.

Before clinical study initiation, this protocol, the informed consent form, any other written information given to subjects, and any advertisements planned for subject recruitment must be approved by an IRB/IEC.

Voluntary informed consent must be obtained in writing from every subject and the process shall be documented before any procedure specific to the clinical investigation is applied to the subject. The Investigator must have a defined process for obtaining consent. [REDACTED]

Short Title:**Statistical Analysis Plan**
CLL949-C009 / NCT03920280**Full Title:****Statistical Analysis Plan** [REDACTED]
CLL949-C009

Protocol Title: Clinical Evaluation of a Daily Wear Frequent Replacement
Silicone Hydrogel Lens

Project Number: [REDACTED]

Reference Number:

Protocol TDOC Number: TDOC-0056233

Author:
[REDACTED]
[REDACTED]

Template Version: [REDACTED]

Approvals: See last page for electronic approvals.

Job Notes:

This is the original (Version 1.0) Statistical Analysis Plan for this study. This version of the Statistical Analysis Plan is based on Version 1.0 of the study protocol.

Executive Summary:

Key Objectives:

The primary objective is to demonstrate safety and effectiveness of [REDACTED] soft contact lens when worn for daily wear as compared to BIOFINITY® soft contact lens.

[REDACTED]

[REDACTED]

Table of Contents

Statistical Analysis Plan - US CLL949-C009	1
Table of Contents	3
List of Tables	4
1 Study Objectives and Design	5
1.1 Study Objectives	5
1.2 Study Description	5
1.3 Randomization	6
1.4 Masking	6
2 Analysis Sets	6
2.1 All Enrolled	6
2.2 Enrolled Dispensed	6
2.3 Enrolled Not Dispensed	7
2.4 Completed	7
2.5 Discontinued	7
3 Subject Characteristics and Study Conduct Summaries	7
4 Effectiveness Analysis Strategy	7
4.1 Effectiveness Endpoints	8
4.2 Effectiveness Hypotheses	8
4.3 Statistical Methods for Effectiveness Analyses	9
4.3.1 Primary Effectiveness Analyses	9
5 Safety Analysis Strategy	10
5.1 Safety Endpoints	10
5.2 Safety Hypotheses	11
5.3 Statistical Methods for Safety Analyses	11
5.3.1 Adverse Events	11

5.3.2	Biomicroscopy Findings/Slit Lamp Examination	12
5.3.3	Device Deficiencies.....	12
	[REDACTED]	
	[REDACTED]	
8	References.....	13
	[REDACTED]	
10	Appendix.....	14

List of Tables

Table 1-1 Study Description Summary	5
Table 10-1 Schedule of Study Procedures and Assessments	14

1 Study Objectives and Design

1.1 Study Objectives

PRIMARY OBJECTIVE

The primary objective is to demonstrate safety and effectiveness of [REDACTED] soft contact lens when worn for daily wear as compared to Biofinity soft contact lens.

1.2 Study Description

Key components of the study are summarized in Table 1-1.

Table 1-1 Study Description Summary

[figure not shown]
Study Design	Prospective, multi-center, randomized, [REDACTED] controlled, double-masked, parallel-group
Study Population	Volunteer subjects aged 18 or over who are adapted daily wear frequent replacement soft contact lens wearers, excluding Biofinity habitual wearers, have at least 3 months of soft contact lens wearing experience, and who wear their habitual lenses at least 5 days per week and at least 8 hours per day. [REDACTED] [REDACTED] [REDACTED] [REDACTED] [REDACTED] Target to complete: 90 subjects (60:30; Test:Control) Planned to enroll: ~120 subjects
Number of Sites	~8 (US)
Test Product	[REDACTED] soft contact lenses [REDACTED]
Control Product	CooperVision® BIOFINITY® (comfilcon A) soft contact lenses (Biofinity)
Duration of Treatment	Approximately 3 months
Visits	Visit 1: Screening/Baseline/Dispense (Day 1) Visit 2: Week 1 Follow-up Visit 3: Week 2 Follow-up Visit 4: Month 1 Follow-up Visit 5: Month 2 Follow-up Visit 6: Month 3 Follow-up/Exit

1.3 Randomization

A member of the Randomization Programming group at Alcon who is not part of the study team will generate the randomized allocation schedule(s) for study lens assignment.

[figure not shown]

Subjects will be randomized in a 2:1 ratio to receive either [REDACTED] or Biofinity contact lenses, respectively. [REDACTED]

1.4 Masking

This study is double-masked.

[figure not shown]
2 Analysis Sets

2.1 All Enrolled

All subjects who have signed the informed consent for the study will be included in the All Enrolled analysis set.

2.2 Enrolled Dispensed

Enrolled Dispensed is a subset of All Enrolled subjects/eyes that have been exposed to study lenses.

[REDACTED]

2.4 Completed

The Completed analysis set consists of Enrolled Dispensed subjects/eyes completing the study.

2.5 Discontinued

The Discontinued analysis set consists of Enrolled Dispensed subjects/eyes not completing the study.

3 Subject Characteristics and Study Conduct Summaries

Demographic information (age, sex, ethnicity, and race), recent lens wearing experience (wear modality, wear success), and habitual lens information will be presented by lens group and overall [REDACTED]

[REDACTED].

[REDACTED]

[REDACTED]
[REDACTED]
[REDACTED]
[REDACTED]
[REDACTED]
[REDACTED]

4 Effectiveness Analysis Strategy

This study defines one primary effectiveness endpoint [REDACTED]

[REDACTED]. Unless otherwise specified, separate summary tables will be presented for the Completed and the Discontinued analysis sets with the following distinction:

- Completed Control (eyes/subjects)
- Completed Test (eyes/subjects)

- Discontinued Control (eyes/subjects)
- Discontinued Test (eyes/subjects)

No inferential testing will be performed on the effectiveness endpoints,

4.1 Effectiveness Endpoints

Primary Endpoint

The primary endpoint is distance visual acuity (VA) with study lenses, collected in Snellen, for each eye. Conversion will be made to the logMAR scale.

100%  100%

10. **What is the primary purpose of the `get` method in the `HttpURLConnection` class?**

4.2 Effectiveness Hypotheses

Primary Effectiveness

No inferences are to be made on the primary effectiveness endpoint; therefore, no hypotheses are formulated.

[REDACTED]

[REDACTED]

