3 PROTOCOL SUMMARY

This will be a prospective, randomized [REDACTED] controlled, double-masked, parallel-group clinical study.

Approximately 8 sites in the US will enroll approximately 120 subjects. Subjects will be expected to attend 6 office visits: Screening / Baseline / Dispense, Week 1 Follow up, Week 2 Follow-up, Month 1 Follow-up, Month 2 Follow-up and Month 3 Follow up/Exit. The total expected duration of participation for each subject is approximately 3 months in this daily wear clinical study. Approximately 80 subjects will be assigned to wear the test lenses and 40 subjects will be assigned to wear the control lenses, [REDACTED]

Subjects and the study personnel conducting the study evaluations will be masked to treatment. Subjects who meet the inclusion and exclusion criteria will be randomized to wear either the test contact lenses [REDACTED] in both eyes or the control contact lenses (Biofinity) in both eyes for 3 months of daily wear exposure. [REDACTED]

[REDACTED]
[REDACTED]
[REDACTED]
[REDACTED]
[REDACTED]
[REDACTED]
[REDACTED].

At the Screening / Baseline / Dispense Visit, study lenses will be dispensed to qualified subjects [REDACTED]

All study lenses will be worn for at least 5 days per week and 8 hours per day in a daily wear modality (eg, will not be worn while sleeping). [REDACTED]

[REDACTED]
[REDACTED]
[REDACTED]

[REDACTED] Regardless of whether the subject is randomized to the test or the control group, CLEAR CARE® Cleaning & Disinfecting Solution (CLEAR CARE) must be used for cleaning and disinfection. [REDACTED]

Investigational product type	Medical Device
Study type	Interventional
Investigational products	Test Product: [REDACTED] soft contact lens Control Product: Biofinity soft contact lens
Purpose and rationale	The purpose of this clinical study is to demonstrate the performance of the investigational [REDACTED] soft contact lens compared to the commercially available Biofinity soft contact lens when worn in a daily wear modality, by assessing visual acuity as the primary variable.
Objective(s)	The primary objective is to demonstrate safety and effectiveness of the [REDACTED] soft contact lens when worn for daily wear as compared to the Biofinity soft contact lens.
Endpoint(s)	Primary Effectiveness 
Distance VA (Snellen) [REDACTED] [REDACTED] [REDACTED] [REDACTED] [REDACTED]

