	
■ [REDACTED]
 
Safety
 
 • AEs • Biomicroscopy • Device deficiencies
Study Design	
This will be a prospective, randomized, [REDACTED] controlled, double-masked, parallel-group, daily wear clinical study. Subject participation in the study will be approximately 14 weeks with approximately 3 months of exposure to study lenses.

Subject population	
Volunteer subjects aged 18 or over who are adapted daily wear frequent replacement soft contact lens wearers, excluding Biofinity habitual wearers, have at least 3 months of soft contact lens wearing experience, and who wear their habitual lenses at least 5 days per week and at least 8 hours per day.
 
[REDACTED]
 
[REDACTED]
 
[REDACTED]
 
[REDACTED]
 
[REDACTED]

Key inclusion criteria (See Section 8.1 for a	
 • Successful wear of spherical daily wear frequent replacement soft contact lenses for distance correction in both eyes during the past 3 months for a minimum of 5 days per week and 8 hours per day.

complete list of inclusion criteria)	
 Manifest cylinder \leq 0.75 D in each eye
Key exclusion criteria (See Section 8.2 for a complete list of exclusion criteria)	
 Wearing habitual contact lenses in an extended wear modality (routinely sleeping in lenses for at least 1 night per week) over the last 3 months prior to enrollment. Monovision contact lens wearers Habitually wearing Biofinity lenses
Data analysis and sample size justification	
[REDACTED]
 
[REDACTED]
 
effectiveness and safety data will be presented separately based upon subject study status of Completed or Discontinued.
 
No formal hypotheses are formulated for the primary effectiveness endpoint, hence no inferential testing will be performed.
 
[REDACTED]
 
[REDACTED]
 
[REDACTED]
 
[REDACTED]
 
[REDACTED]
 
[REDACTED]

Key words	[REDACTED] Biofinity, daily wear, [REDACTED]
Associated materials	
CLEAR CARE Cleaning & Disinfecting Solution will be used for daily cleaning and disinfection.
 
[REDACTED]
 
[REDACTED]
 
[REDACTED]
 
[REDACTED]

Table 3-1 Schedule of Study Procedures and Assessments

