Procedure/ Assessment	Visit 1 Screening/ Baseline/ Dispense	Visit 2 Week 1 Follow-up	Visit 3 Week 2 Follow-up	Visit 4 Month 1 Follow-up	Visit 5 Month 2 Follow-up	Visit 6 Month 3 Follow-up/Exit	Early Exit	USV
	Day 1	Day 7	Day 15	Day 30	Day 60	Day 95		
Informed Consent	✓	-	-	-	-	-	-	-
Demographics	✓	-	-	-	-	-	-	-
Medical History	✓	✓	✓	✓	✓	✓	✓	(✓)
Concomitant Medications	✓	✓	✓	✓	✓	✓	✓	(✓)
Inclusion/ Exclusion	✓	-	-	-	-	-	-	-
Habitual lens information (brand / manufacturer, modality, power, wear success, habitual lens care brand)	✓	-	-	-	-	-	-	-
[REDACTED]	█	█	█	█	█	█	█	█
[REDACTED]	█	█	█	█	█	█	█	█
[REDACTED]	█	█	█	█	█	█	█	█
[REDACTED]	█	█	█	█	█	█	█	█

Procedure/ Assessment	Visit 1 Screening/ Baseline/ Dispense	Visit 2 Week 1 Follow-up	Visit 3 Week 2 Follow-up	Visit 4 Month 1 Follow-up	Visit 5 Month 2 Follow-up	Visit 6 Month 3 Follow-up/Exit	Early Exit	USV
	Day 1	Day 7	Day 15	Day 30	Day 60	Day 95		
Biomicroscopy	✓	✓	✓	✓	✓	✓	✓	(✓)
Randomize	✓	-	-	-	-	-	-	-
IP Dispense	✓	✓	(✓)	(✓)	(✓)	-	-	(✓)
VA w/ study lenses (OD, OS Snellen distance) ¹	✓	✓	✓	✓	✓	✓	✓	(✓)

Printed By:

Print Date:

Procedure/ Assessment	Visit 1	Visit 2	Visit 3	Visit 4	Visit 5	Visit 6	Early Exit	USV
	Screening/ Baseline/ Dispense	Week 1 Follow-up	Week 2 Follow-up	Month 1 Follow-up	Month 2 Follow-up	Month 3 Follow-up/Exit		
	Day 1	Day 7	Day 15	Day 30	Day 60	Day 95		
1								
2								
3								
4								
5								
6								
7								
8								
9								
10								
11								
12								
13								
14								
15								
16								
17								
18								
19								
20								
21								
22								
23								
24								
25								
26								
27								
28								
29								
30								
31								
32								
33								
34								
35								
36								
37								
38								
39								
40								
41								
42								
43								
44								
45								
46								
47								
48								
49								
50								
51								
52								
53								
54								
55								
56								
57								
58								
59								
60								
61								
62								
63								
64								
65								
66								
67								
68								
69								
70								
71								
72								
73								
74								
75								
76								
77								
78								
79								
80								
81								
82								
83								
84								
85								
86								
87								
88								
89								
90								
91								
92								
93								
94								
95								
96								
97								
98								
99								
100								
101								
102								
103								
104								
105								

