5 INTRODUCTION

5.1 Rationale and Background

In this clinical study, the performance of the investigational [REDACTED] contact lens will be compared to the commercially available Biofinity contact lens in a parallel group design to demonstrate the safety and effectiveness of the [REDACTED] contact lens, worn daily [REDACTED]

[REDACTED] as compared to Biofinity contact lens, worn daily [REDACTED]
[REDACTED] The intended use of this contact lens is for vision correction. Therefore, the measurement of distance VA is planned as the primary effectiveness variable.

[REDACTED]

[REDACTED]

[REDACTED]

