5.2 Purpose of the Study

The purpose of this clinical study is to demonstrate the safety and performance of the investigational [REDACTED] soft contact lens compared to the commercially available Biofinity soft contact lens when worn in a daily wear modality, by assessing visual acuity as the primary variable.

At the end of the study, a clinical study report will be prepared in accordance with applicable regulatory requirements and standards.

[REDACTED]

[REDACTED]

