6 STUDY OBJECTIVES

6.1 Primary Objective(s)

Table 6–1 Primary Objective(s)

Objective(s)	Endpoint(s)
Demonstrate safety and effectiveness of [REDACTED] soft contact lens when worn for daily wear as compared to Biofinity soft contact lens.	Primary Effectiveness 
• Distance VA (Snellen)

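### The primary objective is to demonstrate safety and effectiveness against Biofinity, but the visible plan is descriptive and SAP 4.2 bars inference on the primary endpoint: restate the objective, and add a between-lens estimate for effectiveness

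*SAP*

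**What the plan says.** **Objective.** The Protocol Summary (section 3) says "The primary objective is to demonstrate safety and effectiveness of the" test lens, whose name is redacted. In Table 6-1 (section 6.1) the comparison is explicit: "soft contact lens when worn for daily wear as compared to Biofinity soft contact lens". Protocol 12.4.1, the SAP Executive Summary and SAP 1.1 carry the same objective. Protocol 5.1 says that the lens "will be compared to the commercially available Biofinity contact lens in a parallel group design to demonstrate the safety and effectiveness of the" test lens, and 5.2 begins "The purpose of this clinical study is to demonstrate the safety and performance of the investigational" lens, again in comparison with Biofinity.

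**Analysis of the primary endpoint.** SAP 4.2: "No inferences are to be made on the primary effectiveness endpoint; therefore, no hypotheses are formulated". Protocol section 3: "No formal hypotheses are formulated for the primary effectiveness endpoint, hence no inferential testing will be performed". Protocol 12.4.1.1 also plans no hypothesis test. The visible analysis consists of summary statistics (by visit in SAP 4.3.1), tabulated by lens and separately for the Completed and Discontinued sets (protocol 12.4, SAP 4).

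**Safety.** Protocol 12.6 and SAP 5.2 set no safety hypotheses and plan a descriptive assessment. The separate safety objective in Table 6-2 is more modest than the primary objective: it asks that the safety profile be evaluated.

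**Size and data.** Protocol section 3: "Approximately 80 subjects will be assigned to wear the test lenses and 40 subjects will be assigned to wear the control lenses". SAP Table 1-1 targets 90 completers (60 test, 30 control) from about 120 enrolled. The schedule lists "VA w/ study lenses (OD, OS Snellen distance" at all six visits and at Early Exit.

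**The concern.** To say that one lens has been shown safe and effective relative to another is to draw an inference about the two lenses. SAP 4.2 rules that out for the primary endpoint, and nothing visible for safety goes beyond description. If the SAP is followed, the report may set the two groups side by side, but its stated objective asks for more than that.

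The objective is the standard against which the clinical study report will be read. If the wording stays, a reader could take the objective as met because two columns of summary statistics look alike, with no visible rule for how alike they must be and no statement of uncertainty. The safety half is exposed in the same way: similar event counts in groups of this size say little about uncommon events.

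**Working it through.** **1. The plan's own figures.** They agree with each other: 8 sites × 15 subjects = 120; 2:1 allocation of 120 gives 80:40, and of 90 gives 60:30; 90/120 = 75% completing. No alpha, power, SD or margin is visible, so the sample size cannot be tied to any error rate or precision target. Most of the sample-size text in protocol section 3 is redacted, so this is not an omission.

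**2. Objective against analysis.**

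| Part | Objective | Visible analysis |
|---|---|---|
| Effectiveness | Demonstrate, compared with Biofinity (protocol 3, 6.1, 12.4.1; SAP Executive Summary, 1.1) | No inference (SAP 4.2); no hypotheses or testing (protocol 3, 12.4.1.1); summary statistics |
| Safety, in the primary objective | Demonstrate, compared with Biofinity (same places) | No hypotheses; descriptive (protocol 12.6, SAP 5.2) |
| Safety, Table 6-2 | Evaluate | Descriptive: consistent |

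The first two rows do not match; the third does.

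**3. What an effectiveness estimate could show.** Inputs from the documents: 60:30 completers, or at most 80:40. The 80:40 is an upper bound, because the protocol speaks of subjects assigned and defines enrolment as signing consent, so screen failures may come out of the 120. Assumed inputs: eye-level logMAR SD 0.05 to 0.15 and inter-eye correlation ρ 0.3 to 0.8. Averaging the two eyes at one visit:

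- Subject-level SD = SD × √((1+ρ)/2)
- SE = subject-level SD × √(1/n_test + 1/n_control)
- Half-width = t(0.975, n_test + n_control − 2) × SE

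For 60:30, √(1/60 + 1/30) = 0.2236 and t(88) = 1.987. For 80:40, √(1/80 + 1/40) = 0.1936 and t(118) = 1.980.

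| SD, ρ | Subject-level SD | SE, 60:30 | Half-width, 60:30 | Half-width, 80:40 |
|---|---|---|---|---|
| 0.05, 0.3 | 0.0403 | 0.0090 | 0.0179 | 0.0155 |
| 0.10, 0.5 | 0.0866 | 0.0194 | 0.0385 | 0.0332 |
| 0.15, 0.8 | 0.1423 | 0.0318 | 0.0632 | 0.0546 |

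The range is thus about 0.018 to 0.063 at 60:30 and 0.015 to 0.055 at 80:40 (the smallest value is 0.01546 before rounding). A model over several visits would give somewhat different widths.

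**4. What the safety data could exclude.** With no events among n subjects, the one-sided 95% upper limit for the event rate is 1 − 0.05^(1/n).

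- n = 80 (test): 3.7%
- n = 40 (control): 7.2%

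These are the relevant counts if all assigned subjects are exposed, because safety is tabulated for Discontinued as well as Completed subjects. With fewer exposed the limits rise, for example to 4.9% with 60 and 9.5% with 30. They apply to subject-level rates; ocular adverse events are tabulated by eye (SAP 5.3.1).

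**The case against.** The strongest reply is that this is mainly wording. Both documents say openly that neither the primary endpoint nor safety is tested, they agree with each other, and the objective never mentions superiority, equivalence or non-inferiority. It is true that the design needs no hypothesis test and that rewording the objective changes no analysis. But the wording decides what the report may conclude, so the mismatch matters.

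A second reply is redaction. Text is hidden or garbled in the sample-size part of protocol section 3, in protocol 12.4.1.2, and in SAP 4.2 and 4.3.1. The sentences barring inferential testing in protocol 12.4 and SAP 4 break off at a comma. A descriptive between-lens difference, a named visit or a benchmark may be there, and a benchmark might give *demonstrate* a defined descriptive meaning. This stands as a limit on the finding. It does not remove the mismatch: the sentence in SAP 4.2 is complete, and an inferential interval in hidden text would contradict it.

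Three stronger readings are tempting, and the documents do not support them:

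- *The plan has no between-lens comparison, success criterion or sample-size rationale.* Visible text cannot establish this.
- *Both documents forbid all inference.* Only SAP 4.2 does. Protocol section 3 and 12.4.1.1 bar hypotheses and testing, which still leaves room for estimation.
- *Adding a confidence interval would by itself be enough.* It would not. An interval without a criterion stated in advance demonstrates nothing, and it leaves the safety half untouched.

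**Conclusion.** The mismatch is real and rests on complete, unredacted sentences. As visible, the descriptive plan cannot support a conclusion that effectiveness or safety was demonstrated relative to Biofinity. It is an inconsistency between objective and analysis, not a flaw in choosing a descriptive design.

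The figures give scale only, and the conclusion does not depend on them. The logMAR half-widths rest wholly on the assumed SD and correlation and on a single-visit comparison. The safety limits use the planned counts and assume that everyone assigned is exposed. They do not show that the trial is too small, because no precision target or margin is visible against which to judge it.

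**What to change.** **1. Restate the primary objective; this is what cures the mismatch.** In both documents, say that the study evaluates or describes the safety and effectiveness of the test lens alongside Biofinity, with the safety part matching Table 6-2. The places are protocol 3 (purpose and objective), 5.1, 5.2, 6.1 and 12.4.1, and SAP Executive Summary and 1.1. The cost is wording, plus the loss of any claim to have demonstrated safety or effectiveness against Biofinity.

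**2. In addition, for effectiveness only, report an estimate.** Amend SAP 4.2 and 4.3.1 and protocol 3, 12.4 and 12.4.1 to give the test-minus-control difference in mean logMAR distance VA at one named visit, for example Month 3, with a two-sided 95% CI presented as an estimate. Check the parallel sentence that opens SAP 4.

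- Use all evaluable Enrolled Dispensed subjects, Completed and Discontinued together, alongside the separate tables. Evaluability is fixed before unmasking under protocol 12.1, and 12.5 limits the data to evaluable subjects/eyes.
- Account for two eyes per subject and, if several visits are modelled, for repeated measures within eye.
- State how Visit 1 and Early Exit values are handled.
- State the missing-at-random assumption. A likelihood-based model needs no imputation, so that rule in protocol 12.5 can stand.

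This costs one model and one table on data already scheduled, with no more subjects. The downside is that the uncertainty of the comparison becomes visible and that the result rests on an assumption that cannot be verified.

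**3. If the claim to demonstrate effectiveness is kept,** the sponsor must state and justify in advance the criterion against which the interval is read. That is a design choice, and the criterion can be missed; none is proposed here.

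**4. If redacted text already holds an inferential interval,** reconcile it with SAP 4.2.
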